### 7.2. Statistical Analysis of Cosmetic Outcome

The rate of *physician-reported* good/excellent cosmesis will be estimated at baseline and at 6, 12, 24, and 36 months. Assuming an observed good/excellent cosmesis rate of about 0.75, an increase in the sample size from 40 to 100 will allow the width of the 95% confidence interval (CI) of the rate to be decreased by 0.10 units. Specifically, a rate of 0.75 with samples sizes of 40 and 100 has 95% CI's of 0.62 – 0.88 and 0.67 – 0.83, respectively.

A true rate of good/excellent cosmesis of  $\geq 0.80$  would be considered very good, while a rate of  $\leq 0.60$  would be unacceptable. The table below gives a rough guideline for monitoring the 12 month cosmesis rate (the rates at the other time points will not be monitored).

Sample size	Review data if the number of patients with good/excellent cosmetic outcome is:
30	$\leq 21$ ( $21/30 = 0.70$ )
60	$\leq 42$ ( $42/60 = 0.70$ )
100	$\leq 70$ ( $70/100 = 0.70$ )

Simply said, any evidence that the observed cosmesis rate would likely be  $\leq 0.70$  would be cause for review. For example, suppose 30 of the first 50 patients (60%) had good/excellent cosmesis. Then even if the next 10 patients had acceptable cosmesis (40/60), this would not be enough to avoid a review of the data. Therefore, a review would have to be begun when  $N=50$ . The monitoring rules above have high probability (i.e., 0.97) of initiating a review of the cosmetic data if the true probability of having

good/excellent cosmetic outcome is  $\leq 0.60$  and a low probability (i.e., 0.14) of initiating a review if the true probability of a good/excellent cosmetic endpoint is  $\geq 0.80$ .

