## 8. SAFETY MONITORING AND REPORTING

The PI is responsible for the identification and documentation of adverse events and serious adverse events, as defined below. At each study visit, the PI or designee must assess, through non-suggestive inquiries of the subject or evaluation of study assessments, whether an AE or SAE has occurred.

Previously, an interim analysis of the first 17 patients was completed. Delayed wound healing, and an increase in grade 2 seromas, relative to our Phase I experience, were observed. The PI and study team believe that there is an interaction between the radiation and surgery (when completed 6 weeks after protocol treatment) that was not seen with our previous practice of 10 days after protocol treatment. Therefore, with the current amendment, we are returning to the practice established from our phase 1 study (Pro00015617) where minimal toxicities were observed. Whilst adverse events will continue to be monitored vigorously, it is not anticipated that those toxicities will be seen in future enrolled subjects given our prior experience. Therefore, there is no plan to complete an additional interim analysis for this study.

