## **9. QUALITY CONTROL AND QUALITY ASSURANCE**

### **9.1 Monitoring:**

This clinical research study will be monitored both internally by the PI and institutionally by the Duke Cancer Institute (DCI). In terms of internal review the PI will continuously monitor and tabulate adverse events. Appropriate reporting to the Duke University Medical Center IRB will be made. If an unexpected frequency of Grade III or IV events occur, depending on their nature, action appropriate to the nature and frequency of these adverse events will be taken. This may require a protocol amendment, dose de-escalation, or potentially closure of the study. The PI of this study will also continuously monitor the conduct, data, and safety of this study to ensure that:

Stopping rules for toxicity and/or response are met;

Risk/benefit ratio is not altered to the detriment of the subjects;

Appropriate internal monitoring of AEs and outcomes is done;

Over-accrual does not occur;

Under-accrual is addressed with appropriate amendments or actions;

Data are being appropriately collected in a reasonably timely manner.

DCI review and monitoring of this protocol occurs in accordance with the NCI-approved Data and Safety Monitoring Plan. Briefly, protocol review begins with an initial review by the Cancer Protocol Committee (CPC), which assesses the ethics and safety of the protocol. Documentation of these assessments will be maintained. Formal, independent monitoring will be conducted by the DCI Monitoring Team after the first 3 subjects are enrolled, followed by annual monitoring of 1-3 subjects until the study is closed to enrollment and subjects are no longer receiving study interventions that are more than minimal risk. DCI Monitoring Team reports and additional data/safety/toxicity reports submitted by the PI will be reviewed by the Safety Oversight Committee (SOC) on an annual basis. Additional monitoring may be prompted by findings from monitoring visits, unexpected frequency of serious and/or unexpected toxicities, or other concerns. Monitoring visits may also be initiated upon request by DUHS and DCI Leadership, CPC, SOC, a sponsor, an investigator, or the IRB.

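### The 0.97 review probability in Section 7.2 fits only two of the three printed 12-month cosmesis looks (all three give 0.994), and Section 8 should make an exception for those reviews

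*Combined protocol and SAP*

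**What the plan says.** Section 7.2 (Statistical Analysis of Cosmetic Outcome) introduces a table that "gives a rough guideline for monitoring the 12 month cosmesis rate (the rates at the other time points will not be monitored"). The table has three rows. The data are reviewed if good/excellent outcomes number 21 or fewer among 30 patients, 42 or fewer among 60, or 70 or fewer among 100. A worked example at 50 patients shows that a review starts as soon as the next boundary can no longer be avoided.

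The section then gives two operating characteristics. For a true rate of 0.60 or lower, which it calls unacceptable: "The monitoring rules above have high probability (i.e., 0.97) of initiating a review of the cosmetic data". For a true rate of 0.80 or higher, which it calls very good: "a low probability (i.e., 0.14) of initiating a review if the true probability of a good/excellent cosmetic endpoint is" at that level. No probability is given for rates in between. The precision calculation earlier in the same section starts from "Assuming an observed good/excellent cosmesis rate of about 0.75".

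Section 8 (Safety Monitoring and Reporting) describes a completed interim analysis of the first 17 patients, which found delayed wound healing and more grade 2 seromas. It explains the return to surgery within 10 days and concludes that "there is no plan to complete an additional interim analysis for this study". It does not mention the cosmesis looks, and Section 7.2 does not mention Section 8.

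Section 9.1 (Monitoring) lists, among the things the investigator is to ensure, "Stopping rules for toxicity and/or response are met". Section 7.1 says that pathologic response is no longer an endpoint.

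**The concern.** The sentence giving 0.97 and 0.14 refers to the rules printed just above it, and those have three rows. If the figures describe only two of the rows, a reader cannot tell whether the review at 100 patients is part of the rule. This matters because the rule oversees the primary endpoint, and the two probabilities are all the oversight committee has for judging it.

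Two matters of consistency go with this. Section 8 rules out further interim analysis for the whole study, while Section 7.2 sets out reviews of accumulating data at 30 and 60 patients. Section 9.1 points to stopping rules for toxicity or response, but response has been dropped and no numeric toxicity boundary is printed.

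**Working it through.** **Inputs.** From Section 7.2: review if X30 ≤ 21, or X60 ≤ 42, or X100 ≤ 70, where Xn is the number with good/excellent cosmesis among the first n patients evaluated at 12 months. Stated properties: 0.97 at a true rate p = 0.60 and 0.14 at p = 0.80. Patients are taken as independent with a common p.

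**Method.** The cumulative count is followed exactly from look to look, and paths that have already triggered a review are removed:

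P(review) = P(X30 ≤ 21) + P(X30 > 21, X60 ≤ 42) + P(X30 > 21, X60 > 42, X100 ≤ 70).

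The increments are binomial: 30 patients to the first look, 30 more to the second and 40 more to the third.

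**Results** (totals come from unrounded terms).

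| True rate p | First triggered at 30 | First triggered at 60 | First triggered at 100 | Looks at 30 and 60 | All three looks |
|---|---|---|---|---|---|
| 0.60 | 0.9060 | 0.0689 | 0.0187 | 0.9749 | 0.9937 |
| 0.70 | 0.5685 | 0.1127 | 0.0619 | 0.6812 | 0.7430 |
| 0.75 | 0.3264 | 0.0591 | 0.0243 | 0.3855 | 0.4098 |
| 0.80 | 0.1287 | 0.0131 | 0.0022 | 0.1417 | 0.1439 |

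A simulation of 2,000,000 trials per rate agrees: 0.9936, 0.4096 and 0.1436 for three looks at 0.60, 0.75 and 0.80.

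**Reproducing the plan's figures.** The looks at 30 and 60 give 0.9749 and 0.1417, which match the stated 0.97 and 0.14. All three rows give 0.9937 and 0.1439. The 0.14 is reproduced, but 0.97 is missed by 0.9937 − 0.97 = 0.0237. Other readings do not rescue the pair:

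- Boundaries read as strictly below 0.70, three looks: 0.986 and 0.072.
- Looks at 60 and 100 only: 0.991 and 0.046.
- Looks at 30 and 100 only: 0.992 and 0.133.
- The look at 30 alone: 0.906 and 0.129.

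**Early start.** Beginning a review once a boundary is certain to be crossed, as in the example at 50 patients, changes when the review happens but not whether it happens. It leaves every probability above unchanged and cannot explain the 0.97.

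**Direction.** P(review) falls as p rises, so 0.994 is the smallest value over all rates of 0.60 or lower, and 0.144 is the largest over all rates of 0.80 or higher.

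**Sections 8 and 9.1.** These need no arithmetic. Section 7.2 requires data reviews at 30 and 60 patients. The last sentence of Section 8 excludes further interim analysis in study-wide terms and makes no exception. In Section 9.1, the response half of the stopping-rules line refers to an endpoint that Section 7.1 removed. For the toxicity half, the plan gives no numeric boundary, only case-by-case action on an unexpected frequency of Grade III or IV events.

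**The case against.** The plan calls the table a rough guideline, and a crossing prompts a review, not a stop. Both stated figures agree with the looks at 30 and 60, so the likely explanation is that the row at full sample size was left out of the calculation. That is an inference; the documents do not say so. The resulting understatement is small and protective. All of this stands, and it limits the point to correcting a stated figure.

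Four stronger readings are tempting, and the documents do not support them.

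- **The rule falls short of its stated performance.** It does not. At rates of 0.60 or lower the printed rule starts a review with probability at least 0.994, and 0.14 remains correct.
- **The 0.41 at a true rate of 0.75 shows that the rule is faulty.** It contradicts no stated figure, because properties are given only at 0.60 and 0.80 and intermediate values are to be expected between them. The 0.75 is an assumed observed rate for the confidence interval, and the 75-80% in Section 3.3 is a 3-year expectation, whereas the rule monitors 12 months. Reporting the figure would help, but its absence is not an error.
- **Section 8 cancels the cosmesis reviews.** Its sentence closes a paragraph about wound healing and seromas, and Section 7.2 sets out the reviews in detail. Only the breadth of the Section 8 wording conflicts with them.
- **The look at 100 is useless because it comes after everyone is treated.** This ignores the early-start example. A crossing of the third row means at least 30 patients without good/excellent cosmesis. A trial that passed the second look has at most 17 such patients among 60, so the crossing can be certain from patient 60 + 13 = 73. All 100 patients would usually have been treated by then, but the review would still inform interpretation of the primary endpoint.

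On Section 9.1, the leftover response wording is editorial. Toxicity is not ignored: the same section provides for action up to closure of the study, and Section 8.3 provides for annual committee review.

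**Conclusion.** The 0.97 in Section 7.2 is wrong for the rule as printed: three looks give 0.994 at a true rate of 0.60, and the 0.14 at 0.80 holds (0.144). The gap is about 2.4 percentage points in the safe direction. The primary estimate, the sample size and the boundaries are unaffected. The result assumes independent patients with a common true rate, and 12-month outcomes available for the full 30, 60 and 100.

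Section 8 conflicts with Section 7.2 in wording, though its context is toxicity; one clause resolves this. The Section 9.1 line is a minor inconsistency. The 0.41 at a true rate of 0.75 is worth disclosing but is optional.

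**What to change.** 1. **Section 7.2.** Keep all three rows. Restate the probabilities as 0.99 at a true rate of 0.60 or lower and 0.14 at 0.80 or higher, and say that they cover the looks at 30, 60 and 100. Dropping the row at 100 to preserve 0.97 would change the rule and is not recommended as a way to correct the text.
2. **Section 7.2, optional.** Add that a review starts with probability 0.41 at a true rate of 0.75, so that the committee does not take a review by itself as strong evidence of poor cosmesis.
3. **Section 8.** Amend the closing sentence to say that no additional interim analysis is planned other than the 12-month cosmesis reviews in Section 7.2.
4. **Section 9.1, minor.** Reconcile the stopping-rules line with Section 7.1, where response is no longer an endpoint, and with the absence of a numeric toxicity rule. Whether such a rule should apply is for the investigator and the oversight committee; none is proposed here.

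The cost is wording in an amendment. No data collection, boundary or sample size changes.

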### 7.3 Statistical Analyses of the Secondary Objectives

(a) The mean of *patient-reported* rate of good/excellent cosmesis, and its 95% CI, will be estimated at baseline and at 6, 12, 24, and 36 months.

(b) Quality of life (FACT-B) and patient satisfaction will be measured at baseline and at 6, 12, 24, and 36 months. For each scale, the mean and its 95% CI's will be estimated at each time point; boxplots will be used to estimate the distribution of these scales at each time point.

(c) Time to local or regional failure will be defined as the time from start of treatment to date of local or regional failure, whichever comes first; distant failures will be ignored; deaths will be censored. Time to distant failure will be defined as the time from start of treatment to date of distant failure; local and regional failures will be ignored; deaths will be censored. The Kaplan Meier method will be used to estimate both of these distributions.

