##### **Secondary Objectives**

1. Determine patient-reported rates of good/excellent cosmesis at baseline and 6 months, 1, 2, and 3 years post-treatment as measured by the NRG cosmesis scale.
2. Assess patient-reported Quality of Life (FACT-B) and patient satisfaction at the same time points.
3. Assess locoregional control in the treated breast relative to historical controls at 10 years.

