## 6. PATIENT ASSESSMENTS

Assessment	Pre-Tx.	Follow-up
Consent	X	
History/Physical	X	X a
Complete Blood Count (no differential)/CMP	X	
Breast imaging (mammogram minimum)	X	X a
Core Biopsy/Fiducial Markers	X b	
Planning MRI	X	
Surgical Excision with Tissue Procurement		X c
Acute Toxicity Evaluation		X d
Cosmetic Evaluation Form/Digital Photographs/QOL	X e	X e
Clinical Outcomes		X a
Serum collection	X f	X f
Urine collection	X g	X g
BRPC Consent prior to surgery		X h

- a. Physical exam by member of oncology team recommended every 4-6 months for 2 years, every 6 months through year 5 and annually years 5-10. Bilateral mammogram recommended at least annually.
- b. Verify placement of a biopsy clip at diagnostic procedure and availability of pre-treatment tissue for correlative science.
- c. Within 10 days of radiation.
- d. Appointment with the Radiation Oncologist/mid level provider 1-2 months after surgery.
- e. At baseline (prior to treatment), six months and one year after treatment and then annually for 2 additional years. Cosmetic assessment to be filled out by both patient and physician/mid level provider. Digital photographs at the same time points and at investigator's discretion.
- f. 2 lavender tubes drawn prior to radiation therapy and post radiation therapy (before surgery)
- g. Urine collected prior to radiation therapy and post radiation therapy (before surgery)
- h. Subjects will be consented to the existing Biospecimen Repository and Processing Core (BRPC) tissue collection protocol which includes safeguards to ensure adequate tissue for diagnostic evaluation and biomarker assessment

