### **6.1 Screening Examination**

The screening examination can take place up to 45 days before study treatment. An informed consent must be signed by the patient before any screening procedure takes place. If however, standard of care evaluation procedures have been obtained and are within the screening evaluation time points, the SOC procedures do not need to be repeated and may be included in the screening examination. Subject data to be collected includes a complete history and physical including signed informed consent, basic clinical laboratory studies, staging and a biopsy demonstrating ductal carcinoma in situ or invasive breast carcinoma.

Assessment of the tumor by physical exam and mammogram (further imaging at radiologist/physician discretion) should include tumor measurements. Each patient will complete a baseline cosmetic evaluation as will her physician/mid level provider. QOL measures will also be assessed. Prior to study treatment, placement of a biopsy clip at the time of diagnostic biopsy will be verified as this will serve as a fiducial marker (described in section 6.2) to assist in radiotherapy localization. MRI and CT of the affected breast will then be completed for radiation treatment planning

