**2. How satisfied with your treatment are you?**

Extremely satisfied

Very Satisfied

Satisfied

Unsatisfied

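### FACT-B is summarised only visit by visit, with no interval for change after treatment, and a baseline summary is scheduled for satisfaction items that ask about treatment already received

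*Combined protocol and SAP*

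**What the plan says.** Secondary objective 2 (section 3.1) is: "Assess patient-reported Quality of Life (FACT-B) and patient satisfaction at the same time points". The time points are those of secondary objective 1, which include baseline: "Determine patient-reported rates of good/excellent cosmesis at baseline and 6 months, 1, 2, and 3 years post-treatment".

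Section 7.3(b) carries this into the analysis: "Quality of life (FACT-B) and patient satisfaction will be measured at baseline and at 6, 12, 24, and 36 months". The planned output is "For each scale, the mean and its 95% CI's will be estimated at each time point", and "boxplots will be used to estimate the distribution of these scales at each time point". Nothing else is planned for these measures. No section mentions change from baseline, a paired or repeated-measures analysis, or missing questionnaires for quality of life.

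Note e to the assessment table in section 6 fixes the timing of the cosmetic form, photographs and quality of life: "At baseline (prior to treatment), six months and one year after treatment and then annually for 2 additional years". Section 6.1 confirms that quality of life is assessed at screening, so each woman has a pre-treatment FACT-B score.

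The only satisfaction items are questions 2 and 3 of the Patient Self-Assessment in Appendix III. Question 2, "How satisfied with your treatment are you", has four ordered categories. Question 3 asks whether she would choose the treatment again, yes or no. No numeric scores are assigned to either.

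**The concern.** There are two separate matters.

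**FACT-B.** The same women are measured up to five times, in a single-arm trial. A reader of the results will naturally ask whether scores fell or recovered after treatment. The planned output gives a point difference by subtraction but no valid interval for it. The two means come from correlated and possibly only partly overlapping sets of women, and the correlation is not reported. The set of women behind each mean may also change over 3 years. Sections 6.5 and 6.5.1 allow removal from follow-up at the woman's wish and withdrawal for adverse events or disease progression. Section 6.5.3 rules out replacement once radiation has begun. If those who leave score differently from those who stay, the means can move with no individual change.

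**Satisfaction.** A summary at baseline is scheduled for questions that presuppose treatment. Any number produced there would be uninterpretable. At later visits, a mean of the four-category item depends on scores that the plan does not give.

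**Working it through.** The documents state no precision, power or sample size for FACT-B or satisfaction, so there is no figure of the plan's own to reproduce.

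**Inputs from the documents**
- Sample size 100 (section 3.5).
- 95% intervals and visits at baseline, 6, 12, 24 and 36 months (section 7.3(b)).

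**Assumptions, because the documents are silent**
- Within-woman correlation r between baseline and a later visit: 0.3, 0.5 or 0.7.
- Equal SD at both visits, so results are in SD units.
- Two-sided intervals, normal approximation, complete pairs.
- 70 complete pairs as an illustration of attrition.

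**Step 1: interval for change, two routes**
- Two visit means treated as unrelated: half-width = 1.96 × SD × √(2/n).
- Mean within-woman change: half-width = 1.96 × SD × √(2(1 − r)/n).
- Ratio, unrelated to paired: 1/√(1 − r).

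At n = 100, the unrelated half-width is 1.96 × √0.02 = 0.277 SD. Paired at r = 0.5, it is 1.96 × √0.01 = 0.196 SD.

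| r | Paired, n = 100 | Unrelated, n = 100 | Paired, n = 70 | Unrelated, n = 70 | Ratio |
|---|---|---|---|---|---|
| 0.3 | 0.232 SD | 0.277 SD | 0.277 SD | 0.331 SD | 1.20 |
| 0.5 | 0.196 SD | 0.277 SD | 0.234 SD | 0.331 SD | 1.41 |
| 0.7 | 0.152 SD | 0.277 SD | 0.181 SD | 0.331 SD | 1.83 |

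**Step 2: how far a visit mean could move through attendance alone**

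Suppose no woman's score changes, a fraction d stops attending, and their baseline mean is k SD below that of the women who stay. If the stayers' mean is m, the full baseline mean is (1 − d)m + d(m − k) = m − dk. The later mean, taken over stayers, is m. The apparent improvement is therefore d × k SD:
- d = 0.2, k = 0.5: 0.10 SD.
- d = 0.3, k = 0.5: 0.15 SD.

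Both d and k are assumed. This shows what could happen, not what is expected.

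**Step 3: satisfaction at baseline**

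This needs no arithmetic. Section 7.3(b) and objective 2 include baseline for satisfaction. Section 6 note e defines baseline as before treatment. Both Appendix III items ask about treatment received. The schedule and the questions cannot both stand. Section 6.1 says "Each patient will complete a baseline cosmetic evaluation as will her physician/mid level provider" and adds quality of life, without naming satisfaction. The satisfaction items nevertheless sit on the same patient form as the cosmetic rating.

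**The case against.** The strongest reply is that the analysis does what the objective asks. Objective 2 is to assess these measures at listed times. It names no hypothesis, target or change. A mean, interval and boxplot per visit answer it, and each interval is valid for the women assessed at that visit. That stands: the FACT-B part is an omission worth filling, not an error or a contradiction.

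Three further replies also stand.
- A reader might infer from the table that the plan loses 16%, 29% or 45% of its interval width, or the equivalent of many more patients. The documents do not support this. The plan proposes no unpaired interval for change, so no planned result carries that loss. The ratios apply only to someone who compares the published means as if unrelated, and they depend on an assumed correlation.
- A reader might infer that the visit means will drift. The documents give no dropout rate and no link between dropout and quality of life.
- A reader might infer that change from baseline is the only comparison open to a single-arm trial. The protocol uses external references elsewhere: fixed cosmesis rates in section 7.2 and historical controls for locoregional control in objective 3. An external reference for quality of life would be possible, though none is planned.

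On satisfaction, a mean of the yes/no item is not meaningless: coded 0/1, it is the proportion answering yes. A mean of the four-category item could be computed once scores were stated. A worthless baseline value would not distort later summaries. What the reply does not remove is the mismatch between a pre-treatment assessment and questions about treatment received.

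**Conclusion.** The point holds as a minor improvement to a secondary endpoint. Section 7.3(b) gives no valid interval for within-woman change in FACT-B, although the data for one are collected. Comparing visit means as unrelated would widen that interval by 1.20 to 1.83 times for r from 0.3 to 0.7, given equal SDs and complete pairs. The direction holds for any positive correlation. A shift in the means through selective attendance is possible but not shown; 0.10 to 0.15 SD is an illustration under assumed dropout.

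The baseline satisfaction summary is wrong as written, and this rests on the documents alone.

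The primary endpoint, the sample size and the cosmesis monitoring guideline are unaffected.

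**What to change.** In section 7.3(b):

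1. Add mean within-woman change in FACT-B from baseline at 6, 12, 24 and 36 months, each with a 95% CI, from a mixed model for repeated measures using all visits. State that this is valid if data are missing at random given the observed scores.
2. Keep the visit means, their intervals and the boxplots as description.
3. Delete the baseline satisfaction summary. At post-treatment visits only, report the proportion in each category of the four-category item and the proportion answering yes to the other.
4. Align the wording of secondary objective 2, so that satisfaction is assessed only after treatment.

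The cost is a little more analysis work and reliance on the missing-at-random assumption. No new data, visits or patients are needed.

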**3.5 Selection of Subjects and Sample Size:**

Women ages 60 or older with clinically node-negative, 2cm or less, biopsy proven ductal carcinoma in situ or invasive carcinoma will be considered for this trial. Women age 50-59 with a cT1N0 tumor and a low Oncotype score will also be eligible.

The final sample size is 100 subjects. Up to 150 subjects may be consented in order to enroll the target goal of 100. Given the rapid accrual of our previous trial with similar eligibility (approximately 30/32 subjects over 2 years), we anticipate completion of this trial in 5 years.

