## 4. SUBJECT ELIGIBILITY

### 4.1 Inclusion Criteria:

1. Women with a biopsy proven diagnosis of ductal carcinoma in situ or invasive carcinoma of the breast
  - a. Biopsy tissue (either slides or block) from outside institutions will be reviewed to confirm diagnosis.
2. Breast preservation candidates (no prior breast or nodal radiotherapy, no imaging evidence of multicentric or multifocal disease, no pregnant women, and no comorbid conditions precluding surgery)
3. Clinical T1N0M0 invasive carcinoma or DCIS  $\leq$  or equal to 2cm
4. 60 years of age or older or 50-59 with a low (0-17) Oncotype score . Oncotype is not required for women diagnosed with DCIS.
5. ER+, HER2- (HER2 status is not required for women diagnosed with DCIS)
6. Women of child-bearing potential must consent to use adequate contraception during the course of the study. Female subjects must agree to use a medically acceptable contraceptives including: (1) surgical sterilization (such as a tubal ligation or hysterectomy), (2) approved hormonal contraceptives (such as birth control pills, patches, implants or injections), (3) barrier methods (such as a condom or diaphragm) used with a spermicide, or (4) an intrauterine device (IUD). Contraceptive measures such as Plan B (TM), sold for emergency use after unprotected sex, are not acceptable methods for routine use.
7. WBC  $> 3000$ , Hgb  $> 9$ , platelets  $> 100000$  within 45 days of consent
8. MRI is required for radiation treatment planning on this study. A diagnostic MRI performed within 60 days of obtaining consent is acceptable and will not be repeated. Subjects who have not had a diagnostic MRI will be required to have a research treatment planning MRI with contrast ordered by a radiation oncologist; these subjects must have a GFR  $\geq 60$  ml/min.
9. Outside breast imaging will be reviewed at Duke to confirm findings are consistent with trial eligibility.

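### Section 7.3(c) estimates locoregional and distant failure by Kaplan-Meier with deaths censored, so over 10 years 1-KM will overstate, modestly, the probability that a treated woman actually fails, and the plan does not say which estimator lies behind the historical rate.

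*Combined protocol and SAP*

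**What the plan says.** Section 7.3(c) defines two time-to-event endpoints.

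- Locoregional: "Time to local or regional failure will be defined as the time from start of treatment to date of local or regional failure", whichever of the two comes first. The handling of other events is "distant failures will be ignored; deaths will be censored".
- Distant: time from start of treatment to distant failure, with "local and regional failures will be ignored; deaths will be censored".

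The estimator is the same for each: "The Kaplan Meier method will be used to estimate both of these distributions". No competing-risk estimator appears anywhere in the document.

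The third secondary objective in Section 3.1 is "Assess locoregional control in the treated breast relative to historical controls at 10 years". Section 7.3 names no historical rate, no estimator for that rate and no method of comparison. Distant failure is not among the listed objectives.

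Eligibility (Section 4.1) is "60 years of age or older or 50-59 with a low (0-17) Oncotype score", with Oncotype not required for DCIS and no upper age limit. Section 3.5 states "The final sample size is 100 subjects". Section 6.4 schedules visits to year 10, although Section 3.6 puts time on study at about 3 years, with standard-of-care follow-up after that.

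**The concern.** A woman who has died cannot later have a local, regional or distant failure. Censoring her at death treats her as someone who could still fail and would do so at the rate of the women still alive. The complement of the Kaplan-Meier curve is then the failure risk in a hypothetical population in which nobody dies. A clinician or patient shown a 10-year failure percentage will usually take it as the chance that failure happens, and for that reading 1-KM is too high. With a 10-year horizon and an older population, some deaths before failure should be expected.

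Two things are at stake. One is the absolute risk that the trial will be quoted for. The other is the historical comparison of locoregional control. If the historical figure is a cumulative incidence and the trial's figure is 1-KM, the two measure different quantities and the mismatch counts against the study treatment. If the historical figure is itself 1-KM, they measure the same quantity. The plan does not let the reader tell which applies.

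**Working it through.** **Nothing to reproduce.** The document states no failure rate, mortality, event count or precision for these endpoints. Section 3.3 B says only that local recurrence is low after careful selection. All rates below are therefore assumptions, shown over a range.

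**Inputs**
- n = 100 (Section 3.5) and a horizon of 10 years (Section 3.1).
- F, the 10-year failure probability if nobody died, which is what 1-KM targets: assumed 5% and 10%, with a wider range of 2-15%.
- D, the 10-year probability of death without failure: assumed 15-30%, with a wider range of 5-40%.
- Independent, constant hazards.

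**Formulas**
- Failure hazard: λ = -ln(1-F)/10. Death hazard: μ = -ln(1-D)/10.
- 1-KM at 10 years = F.
- Cumulative incidence at 10 years: CIF = λ/(λ+μ) × [1 - exp(-10(λ+μ))], where exp(-10(λ+μ)) = (1-F)(1-D).
- Binomial standard error: √[F(1-F)/100].

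**Worked case, F = 5% and D = 20%**
- λ = 0.05129/10 = 0.005129 and μ = 0.22314/10 = 0.022314.
- λ/(λ+μ) = 0.005129/0.027444 = 0.1869.
- 1 - 0.95 × 0.80 = 0.24.
- CIF = 0.1869 × 0.24 = 0.0449, or 4.49% against a 1-KM of 5.00%.
- Excess 0.51 points. Standard error √(0.05 × 0.95/100) = 0.0218, or about 2.2 points.

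**Over the assumed mortality range**

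| D | CIF when 1-KM = 5% | Excess (points) | 1-KM / CIF | CIF when 1-KM = 10% |
|---|---|---|---|---|
| 10% | 4.75% | 0.25 | 1.05 | 9.50% |
| 15% | 4.62% | 0.38 | 1.08 | 9.24% |
| 20% | 4.49% | 0.51 | 1.11 | 8.98% |
| 30% | 4.21% | 0.79 | 1.19 | 8.44% |
| 40% | 3.92% | 1.08 | 1.27 | 7.87% |

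Across the wider ranges (F 2-15%, D 5-40%) the excess runs from 0.05 to 3.2 points and the ratio from 1.03 to 1.28. It stays below one standard error throughout. The largest case, F = 15% with D = 40%, gives 3.17 points against a standard error of 3.57.

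**Sensitivity.** With a death hazard that doubles every 8 years, F = 5% and D = 20% give a CIF of 4.56% (ratio 1.10), so the excess is slightly smaller.

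**Simulation** (n = 100, 20,000 runs, constant hazards, censoring at 10 years). Mean 1-KM and mean cumulative incidence were 5.03% and 4.51% for F = 5%, D = 20%, and 9.99% and 8.43% for F = 10%, D = 30%. Both agree with the formulas.

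**Effect on the historical comparison.** Suppose the trial and the historical series had identical hazards, with F = 5% and D = 20%. A trial 1-KM set against a historical cumulative incidence would read 5.0% against 4.5%, a spurious disadvantage of about 0.5 points. A trial cumulative incidence set against a historical 1-KM would show a spurious advantage of the same size. With matched estimators the difference is zero.

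**The case against.** The strongest reply is that the plan openly defines a legitimate quantity. If death is independent of failure, Kaplan-Meier with deaths censored estimates net failure, which is a recognised measure of local control, and the objective does not say that a crude probability is wanted. This stands. The overstatement exists only when the figure is read as the actual probability of failure, and a plan that matched a Kaplan-Meier historical rate would compare like with like.

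It is also true that the gap is small against sampling error and that no threshold or test depends on it. Section 5.2 records recurrence in mastectomy patients separately, so the analysed number may be below 100 and the standard error larger than shown. The gap is nevertheless systematic, and a larger sample would not remove it.

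A reader might infer more than the documents support:

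- That 1-KM shifts with other-cause mortality and so distorts the comparison. Under independent hazards the reverse holds: 1-KM stays at 5.0% while the cumulative incidence moves from 4.62% to 4.21% as mortality goes from 15% to 30%. This is a reason to keep both estimates.
- That distant failure is also set against historical controls. Section 3.1 compares locoregional control only.
- That a planned confidence interval is mis-centred. Section 7.3(c) plans none; intervals are named for the secondary objectives only in 7.3(a) and (b).
- That other-cause deaths will outnumber recurrences. The documents give neither rate, nor the expected age mix.
- That breast-cancer deaths without a dated metastasis should be counted as distant failures. That would redefine the endpoint and need cause-of-death data, whose collection the documents do not describe.

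**Conclusion.** The point holds in limited form. Both failure endpoints are to be estimated by Kaplan-Meier with deaths censored, no competing-risk estimate is planned, and over 10 years 1-KM exceeds the probability that a treated woman actually fails. The direction follows from the method. The size rests on assumed rates and constant independent hazards: 0.4-0.8 points at a 1-KM of 5% with 10-year mortality of 15-30%, or 8-19% in relative terms, and below one standard error at n=100. Less complete follow-up beyond year 3 would leave the 10-year estimate less precise than this.

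For locoregional control, the larger gap is that neither the historical rate nor its estimator is named, so it cannot be judged whether the comparison is like with like. The primary cosmesis endpoint is unaffected.

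**What to change.** In Section 7.3(c):

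1. Report the cumulative incidence (Aalen-Johansen) of locoregional failure and of distant failure, with death as a competing event, and give the 10-year estimate with its 95% CI.
2. Keep the Kaplan-Meier estimates alongside, described as net failure with deaths censored.
3. Name the historical locoregional rate, its source and the estimator used there, and make the comparison with that same estimator.

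The cost is a few sentences in the plan, a few lines of code, one extra analysis and two estimates to explain in the report. Censoring at death already requires dates of death, so no new data are needed. Patient care and study procedures do not change.
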